7 SAFETY VARIABLES AND ANALYSES

7.1 Overview of safety analyses including subgroup analyses

For categorical variable, the incidence of subjects by category will be summarized by using frequency counts, and percentages.

Continuous variables will be summarized using: arithmetic mean, SD, minimum, 1st quartile, median, 3rd quartile, and maximum.

No sub-group analyses are planned for safety data.

In addition to the treatment groups indicated in below sections, summaries will report results for the *Total ACT-246475* group.

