1.4 Purpose and rationale of the study

ACT-246475 is a potent, short-acting, reversible, and selective antagonist of the platelet P2Y₁₂ receptor, which is a validated target for the treatment and prevention of arterial thrombosis. ACT-246475 has shown a favorable PK/PD and safety profile in animal models, confirmed in studies conducted in healthy subjects. This Phase 2 study is conducted in subjects with atherosclerotic disease to generate data which are critical for dose selection in future clinical trials in the target AMI population. The impact of 2 different doses and 2 different sites of injection (abdomen vs thigh) on the PD, PK, safety and tolerability of ACT-246475 will be assessed.

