2.2 Other objectives

The other objectives of this study, following a single s.c. administration of ACT-246475, are:

- To assess the PK of ACT-246475.
- To assess the impact of the injection site location (thigh vs abdomen) on the PK and PD of ACT-246475.
- To investigate the impact of concomitant drug use, age, sex, and other covariates on the PK and PD of ACT-246475.
- To investigate the safety and tolerability of ACT-246475.

[figure not shown]

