5.1.4 Study treatment preparation and administration

Detailed information about the study treatment preparation and stability of the solutions is provided within the study treatment handling manual.

The preparation of the study treatment must be done under aseptic conditions by a pharmacist or an authorized person according to local regulation.

The sealed glass vials containing the study treatment will be reconstituted with 1 mL of water for injection. The resulting stock solutions will be at a concentration of 20 mg/mL ACT-246475. For subjects randomized to receive the 8 mg dose of ACT-246475 or its matching placebo, dilution of the stock solution will be performed with 1 mL of NaCl 0.9% to obtain the required concentration for injection [Table 1]. For all doses, the total volume administered will be 0.8 mL (i.e., concentration of the solutions adapted).

The reconstituted ACT-246475 solution will be injected as s.c. single dose in the anterior mid-thigh skin or abdomen skin through [REDACTED] needle. The injected volume will be 0.8 mL for all subjects [REDACTED].

The protocol-mandated study treatment administration procedures may not be altered without prior written approval from the sponsor. An accurate record of the date and amount of study treatment administered to each subject must be available for inspection at any time.

In [Table 1](#), the preparation of doses of the study treatment is described; detailed instructions are given in the study treatment handling manual.

The date and start time of preparation of the injection solution as well as the procedure must be recorded on source documents.

Table 1 Preparation of study treatment for subcutaneous administration

Study treatment	Dose	Volume of water for injection	Volume of NaCl 0.9%	Stock solution concentration	Aliquot of stock solution to be administered
ACT-246475 or placebo	8 mg	1 mL	1 mL	10 mg/mL	0.8 mL
ACT-246475 or placebo	16 mg	1 mL	-	20 mg/mL	0.8 mL

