6.8.2.4 Subgroup analyses

Descriptive summaries will be provided for each secondary PD endpoints using the same sub-groups as defined in Section 6.8.2.4.

Descriptive statistics will also be provided for secondary PD endpoints by injection site sub-group.

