6.9 Analysis of pharmacokinetic variables

The PK variables will be summarized and listed using the PK set.

The plasma PK parameters of ACT-246475 will be derived by non-compartmental analysis of the plasma concentration-time profiles. PK endpoints include: maximum observed plasma concentration (C_{max}), time to reach C_{max} (t_{max}), and the area under the plasma concentration-time curve from time zero to 24 h time point (AUC_{0-24h} ; study drug administration to 24 h time point post administration).

Log-transformed value of C_{max} and AUC_{0-24h} , will be used in the analysis.

The PK parameters (linear and log-transformed ones) will be summarized by dose group using descriptive statistics, i.e., arithmetic mean, SD, geometric mean, minimum, median, maximum, standard error, and 2-sided 95% CI of the means and coefficient of variation in %. Graphical representation of PK results over time (scheduled time point) will be provided using box-whisker plots. For t_{max} , the geometric mean and its 95% CI will not be calculated.

PK variables summary will be provided by dose, injection site, PRU category used for stratification, and by gender.

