8.1.1 Treatment groups

The study included the following 8 *randomization groups* corresponding to the combination of the four study treatment groups (i.e., ACT-246475 8 mg, ACT-246475 16 mg, and their matching placebos) and two injection sites (thigh and abdomen).

The main purpose of this randomization strategy was to balance treatment as well as site of injection assignment. For the analysis, the study treatment arms will consist of the treatment arms: *Placebo*, *ACT-246475 8 mg*, and *ACT-246475 16 mg*. The placebo treatment arm combines the two placebo dose-matching groups.

All analyses, unless stated otherwise, will be reported by those 3 treatment arms, and in this order.

In all Tables, Figures and Listings, treatment groups will be labeled using treatment label [last column of [Table 6](#)].

Table 6 Randomization groups and treatment group labels

Randomization groups		Treatment groups (labels for outputs)
Treatment	Injection site	
ACT-246475 8 mg	Thigh	ACT-246475 8 mg
ACT-246475 8 mg	Abdomen	
ACT-246475 16 mg	Thigh	ACT-246475 16 mg
ACT-246475 16 mg	Abdomen	
Placebo matching ACT-246475 8 mg	Thigh	Placebo
Placebo matching ACT-246475 8 mg	Abdomen	
Placebo matching ACT-246475 16 mg	Thigh	
Placebo matching ACT-246475 16 mg	Abdomen	

Some analyses may require displaying some of the following groups: *Screened failure* subjects group, *Total randomized* (i.e., any subject who has been assigned a study treatment), *Total ACT-246475* group (i.e., subjects randomized to either ACT-246475 8 or 16 mg arms), and *Total* (i.e., all subjects screened).

The order of the treatment group in the statistical report, would then be: Screened failures, ACT-246475 8 mg, ACT-246475 16 mg, Total randomized, Total ACT-246475, and Total.

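### No planned safety summary shows local reactions by thigh versus abdomen, although the protocol says injection site will be assessed for safety, and pooling the placebos leaves dose and vehicle inseparable for that endpoint

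*SAP*

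**What the plan says.** Protocol 1.4 says that the impact of the two doses and of "2 different sites of injection (abdomen vs thigh) on the PD, PK, safety and tolerability of ACT-246475 will be assessed". The formal objectives in Protocol 2.2 are narrower. One is "To assess the impact of the injection site location (thigh vs abdomen) on the PK and PD of ACT-246475"; safety is a separate, general objective, "To investigate the safety and tolerability of ACT-246475". Protocol 3.1 randomises subjects to eight combinations of treatment, dose and injection site.

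The SAP carries injection site into PD and PK. Section 6.8.1.2 gives responder proportions by site, section 6.8.2.4 says "Descriptive statistics will also be provided for secondary PD endpoints by injection site sub-group", and section 6.9 says "PK variables summary will be provided by dose, injection site, PRU category used for stratification, and by gender". For safety, section 7.1 says "No sub-group analyses are planned for safety data".

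SAP 8.1.1 makes three arms the default for all reporting and adds that "The placebo treatment arm combines the two placebo dose-matching groups". SAP 7.2.1.9 defines administration-site reactions as an adverse event of special interest (AESI), and Table 5 tabulates them by preferred term only.

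On preparation, Protocol 5.1.4 and its Table 1 reconstitute every vial with 1 mL water for injection. For the 8 mg dose "or its matching placebo, dilution of the stock solution will be performed with 1 mL of NaCl 0.9" per cent; the 16 mg dose and its placebo have no such step. Every subject receives 0.8 mL.

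**The concern.** Local reaction at the injection site is the safety outcome most directly tied to where the injection is given. Site is randomised, an AESI is defined for it, and the protocol's rationale says site will be assessed for safety. Yet the planned summaries average thigh and abdomen together. Protocol 1.1 gives self-injection as the development goal, so a site difference in tolerability is of practical interest.

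The second part concerns how the dose comparison would be read. The two doses are given in different vehicles, and the dose-matched placebos are the only groups that show each vehicle without drug. Once they are merged, a vehicle difference in local reactions would look like a difference between doses of the drug.

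**Working it through.** **1. Is injection site covered by the safety exclusion?** SAP 6.8.2.4 itself calls injection site a sub-group, so the statement in 7.1 covers it. Where the SAP wants to depart from three-arm reporting it says so: screening status by randomisation group (5.1.1), PD by site (6.8.1.2, 6.8.2.2, 6.8.2.4) and PK by site (6.9). Nothing in section 7 does. SAP section 11 records one change, to the 8-hour platelet variable, and nothing about safety by site.

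**2. Planned group sizes.** Inputs are N = 324 and the ratio 2:2:2:2:1:1:1:1, whose weights sum to 12.

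- Active dose-by-site group: 324 × 2/12 = 54.
- Placebo dose-by-site group: 324 × 1/12 = 27.
- Check: 4 × 54 + 4 × 27 = 324, which reproduces the figures in the randomisation diagram of SAP Appendix A.
- Each arm therefore splits into thigh 54 and abdomen 54. Placebo also splits into 54 matched to 8 mg and 54 matched to 16 mg.

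**3. What pooling does.** Let v8 and v16 be the local-reaction rates of the two vehicles, and d8 and d16 the amounts added by the drug on the risk-difference scale.

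- Pooled placebo = (54·v8 + 54·v16)/108 = (v8 + v16)/2.
- 8 mg minus pooled placebo = d8 + (v8 − v16)/2.
- 16 mg minus pooled placebo = d16 + (v16 − v8)/2.
- 16 mg minus 8 mg = (d16 − d8) + (v16 − v8).
- Each dose minus its own placebo = d8 and d16, with no shift.

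The documents give no local-reaction rates. The vehicle rates below are assumptions, with no drug effect (d8 = d16 = 0):

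| v8 | v16 | Pooled placebo | 8 mg appears | 16 mg appears |
|---|---|---|---|---|
| 5% | 5% | 5% | 0 | 0 |
| 5% | 10% | 7.5% | −2.5 points | +2.5 points |
| 5% | 15% | 10% | −5 points | +5 points |
| 5% | 25% | 15% | −10 points | +10 points |

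**4. What the extra table could show.** The 95% half-width for a difference is 1.96·√[p(1−p)(1/n1 + 1/n2)], with p assumed between 5% and 20%:

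| Contrast | n1 vs n2 | Half-width, points |
|---|---|---|
| Thigh vs abdomen, both active doses together | 108 vs 108 | 5.8 to 10.7 |
| Thigh vs abdomen within an arm, or one placebo vs the other | 54 vs 54 | 8.2 to 15.1 |
| One dose vs its own placebo | 108 vs 54 | 7.1 to 13.1 |
| One dose at one site vs its matched placebo cell | 54 vs 27 | 10.1 to 18.5 |

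With no events, the exact two-sided 95% upper limit, 1 − 0.025^(1/n), is 6.6% for n = 54 and 12.8% for n = 27. These sizes support counts and percentages within arm. They give little reason for formal intervals across all eight cells.

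**The case against.** The strongest reply is that the SAP follows the parts of the protocol that govern analysis. The formal objectives link site only to PK and PD. The safety endpoints in Protocol 6.3 include no local-tolerability endpoint. Protocol 10.3 sets analysis by three arms, and 10.3.4 plans no safety output by site. This stands: the commitment rests on one sentence of the rationale, so a reader who inferred that a formal objective had been dropped would go too far.

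Four other inferences also fail:

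- **That dose is missing from the safety analysis.** Dose is a reporting arm, not a subgroup, and SAP 7.1 does not remove it.
- **That pooling is a departure made by the SAP.** Protocol 10.5 already defines one placebo arm made of both matching groups.
- **That the vehicles are known to differ.** No document says so. The only itemised subcutaneous data, Part A of the healthy-volunteer study in Protocol 1.3.2.3, list no injection-site reaction among 48 subjects (upper limit 1 − 0.025^(1/48) = 7.4%). The vehicle used there is not described, so this neither confirms nor excludes a difference.
- **That local tolerability by site cannot be recovered.** Site and placebo type are in the randomisation data, and SAP 7.2.2 plans AESI listings. The group labels set for listings in 8.1.1 are the three pooled ones, however, and the full output list (SAP section 12) is a separate document not available here.

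It is also true that qualified staff give the injections in this exploratory trial. None of this supplies the missing summary.

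**Conclusion.** The concern holds in a limited form. Protocol 1.4 says injection site will be assessed for safety and tolerability, the trial randomises it, and no summary planned in the SAP text shows administration-site reactions by thigh versus abdomen. SAP section 11 gives no reason.

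The vehicle point is conditional. If the two vehicles differ in local tolerability, the comparison of each dose with pooled placebo shifts by half that difference, in opposite directions for the two doses, and the 16 mg versus 8 mg contrast shifts by the whole of it. If they do not differ, the shift is zero. The calculation assumes equal placebo groups as planned and additive effects on the risk-difference scale; the vehicle rates in it are illustrative.

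The primary PD analysis is not affected. The argument concerns local reactions only and gives no ground for splitting haemorrhage or other safety data by site or by placebo group.

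**What to change.** In SAP 7.1 and Table 5, make one exception to the rule against safety subgroups. Add a descriptive table (n and %) of treatment-emergent administration-site reactions by injection site within each arm, with placebo also shown by its two dose-matching groups. Keep the three-arm tables, with the total active group, for all other safety data, including haemorrhage. Enter the addition in SAP 11.4. If the sponsor prefers not to add it, SAP section 11 should say why the statement in Protocol 1.4 is not carried through.

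The cost is one extra table from data already collected, with no additional subjects or assessments. Counts will be low, so it should be labelled descriptive, without tests.

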7.2 Adverse events

The handling of missing or incomplete date/time of adverse events (AEs) and assessments is described in [Appendix D](#).

7.2.1 Variables

7.2.1.1 All adverse events

An AE is defined as any event that is recorded on the AE eCRF module regardless of the onset date.

7.2.1.2 Treatment-emergent adverse events

Treatment-emergent AEs (TEAEs) are those AEs with onset date/time \geq date/time of study drug administration and \leq 48 h after date/time of study treatment administration.

AEs for which time of onset is missing will still be counted as treatment emergent if onset date is \geq date of study drug administration and is \leq date of study treatment administration +2 days.

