3.1.1 Study periods

The study comprises the following consecutive periods:

Screening period: Lasts 1–21 days; starts with the signature of the informed consent form (ICF) and ends on Day –1.

[figure not shown]
Treatment period: Lasts 2 days: Day 1 and Day 2.

Follow-up period: Lasts 28–35 days (i.e., 30–37 days after single administration of study drug). Starts on Day 3 and ends with the safety follow-up telephone call.

The visit schedule and protocol-mandated procedures will be performed according to the table of assessments [Table 2 and Table 3] and are described in Section 7.

The overall study design is depicted in Figure 2.

Figure 2 Study design

EOS = End of study; ICF = Informed consent form

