9 SAFETY DEFINITIONS AND REPORTING REQUIREMENTS

9.1 Adverse events

9.1.1 Definition of adverse events

An AE is any untoward medical occurrence, i.e., any unfavorable and unintended sign, including an abnormal laboratory finding, symptom, or disease that occurs in a subject during the course of the study, whether or not considered by the investigator as related to study treatment.

A TEAE is any AE temporally associated with the use of study treatment until 48 h after study treatment administration whether or not considered by the investigator as related to

study treatment. The 48-h window for TEAEs has been defined to include at least 5 half-lives of ACT-246475.

AEs include:

- Exacerbation of a pre-existing disease.
- Increase in frequency or intensity of a pre-existing episodic disease or medical condition.
- Disease or medical condition detected or diagnosed during the course of the study even though it may have been present prior to the start of the study.
- Continuous persistent disease or symptoms present at study start that worsen following the signing of informed consent.
- Abnormal assessments, e.g., change on physical examination, ECG findings, if they represent a clinically significant finding that was not present at study start or worsened during the course of the study.
- Laboratory test abnormalities if they represent a clinically significant finding, symptomatic or not, which was not present at study start or worsened during the course of the study.

Overdose, misuse, abuse of the study treatment and study treatment errors will be reported as an AE.

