9.1.2 Intensity of adverse events

The intensity of clinical AEs is graded on a 3-point scale (mild, moderate, severe) and is reported on specific AE pages of the CRF.

All changes in intensity of an AE during the study will be reported in the CRF.

The three categories of intensity are defined as follows:

Mild

The event may be noticeable to the subject. It does not usually influence daily activities, and normally does not require intervention.

Moderate

The event may make the subject uncomfortable. Performance of daily activities may be influenced, and intervention may be needed.

Severe

The event may cause noticeable discomfort, and usually interferes with daily activities. The subject may not be able to continue in the study, and treatment or intervention is usually needed.

A mild, moderate, or severe AE may or may not be serious [see Section 9.2.1]. These terms are used to describe the intensity of a specific event. Medical judgment should be used on a case-by-case basis.

Seriousness, rather than intensity assessment, determines the regulatory reporting obligations.

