9.1.4 Reporting of adverse events

All AEs with an onset date after signing of informed consent and up to 30 days after study treatment administration must be recorded on specific AE pages of the CRF.

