10.2.3 Safety variables

10.2.3.1 Adverse events

An AE is defined as any event that is recorded on the AE CRF module regardless of the onset date.

TEAEs are those AEs with onset date/time \geq date/time of first study treatment administration and \leq 48 h after date/time of last study treatment administration.

The handling of missing or incomplete date/time of AEs and assessments will be described in the SAP.

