7.2.1.4 Treatment-emergent adverse events by intensity

AE intensity is reported by investigator using the following severity scale: mild, moderate, or severe.

For AEs with multiple intensities reported, the worst reported severity will be considered. If the intensity is missing, the AE will be considered as severe.

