7.4 Laboratory tests

7.4.1 Measurements

Only laboratory data received from the central laboratory [see protocol section 7.2.5.2] will be included in the analyses described in this section.

However, laboratory data received from local laboratories will be included in the listings.

Treatment-emergent laboratory abnormalities are central laboratory abnormalities for which blood sample collection were collected on the day of study drug administration or after, and up to the first 48 hours (2 days) after study administration, and that were not present at baseline.

Shift tables of on-treatment value vs baseline, for selected laboratory variables, may be provided according to results.

For each variable, the severity is based on the position of the value against reference ranges (central laboratory) and additional thresholds for significance [see [Appendix C](#)] and the worst abnormality is considered in each direction separately (lowest and highest).

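### Treatment-emergence is decided by onset alone, so an AE that starts between consent and injection and worsens within 48 h after it has no place in the AE summary tables

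*SAP*

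**What the plan says.** **Classification.** The SAP rule is "Treatment-emergent AEs (TEAEs) are those AEs with onset date/time" between administration and 48 h after it (SAP 7.2.1.2). The protocol's statistical section matches: "TEAEs are those AEs with onset date/time" in that interval (Protocol 10.2.3.1). SAP 7.2.1.6 repeats the rule for treatment-emergent SAEs and SAP 7.2.1.9 for the two AESIs. SAP 7.2.1.5 makes an AE non-treatment-emergent only if its onset is 48 h or more after administration. Table 5 has two columns, for onset in the treatment period and onset in the safety follow-up period.

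**Collection.** Protocol 9.1.4: "All AEs with an onset date after signing of informed consent and up to 30 days after study treatment administration must be recorded". Screening lasts 1 to 21 days and "starts with the signature of the informed consent form (ICF") (Protocol 3.1.1).

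**Intensity.** Protocol 9.1.2: "All changes in intensity of an AE during the study will be reported in the CRF". SAP 7.2.1.4: "For AEs with multiple intensities reported, the worst reported severity will be considered".

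**Safety section of the protocol.** Protocol 9.1.1 is worded more broadly: "A TEAE is any AE temporally associated with the use of study treatment until 48 h after study treatment administration". It does not mention worsening within the TEAE definition, although its list of what counts as an AE does include several kinds of worsening.

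**Laboratory.** SAP 7.4.1 requires emergent abnormalities to fall in the 48 h window "and that were not present at baseline". Protocol 10.2.3.2 uses the window alone.

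**The concern.** AEs can start before the injection, because collection begins at consent and blood is drawn both at screening and on Day 1 before dosing. The plan expects one AE to carry several intensities, but it uses them only to choose the worst grade and never to decide whether the event is treatment-emergent. A puncture-site haematoma that is mild before dosing and enlarges afterwards would then be missing from the haemorrhage AESI table.

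Bleeding is the main risk the protocol names for this drug class (Protocol 1.5.1), and this is the first study of the compound in patients. At stake is the completeness of the summary tables that describe that risk.

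**Working it through.** No arithmetic applies. The check takes one case through each rule.

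**Case.** Onset after consent and before injection, with a complete onset date and time. Mild before dosing, severe 6 h after it, one CRF record.

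| Rule | Requirement | Met? |
|---|---|---|
| TEAE (SAP 7.2.1.2, Protocol 10.2.3.1) | Onset from dosing to 48 h | No |
| Treatment-emergent SAE (SAP 7.2.1.6) | Same | No |
| Treatment-emergent AESI (SAP 7.2.1.9) | Same | No |
| Non-treatment-emergent AE (SAP 7.2.1.5) | Onset 48 h or more after dosing | No |
| Non-treatment-emergent AESI (SAP 7.2.1.9) | Onset after dosing | No |
| Non-treatment-emergent AE leading to death (SAP 7.2.1.7) | Onset after dosing | No |
| Table 5 | Onset in treatment or follow-up period | In neither column |
| AE listing (SAP 7.2.2) | All AEs | Yes |

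One entry is less clear. SAP 7.2.1.6 calls post-dose SAEs that are not treatment-emergent non-treatment-emergent, without using the word onset. Even if an AE that turns serious after dosing were placed there, it would be labelled non-emergent, and the follow-up column of Table 5 still asks for onset in that period.

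**Does another convention rescue the case?**
- SAP 7.2.1.2 counts an AE dated on the day of dosing with no onset time as treatment-emergent. Appendix D moves partial onset dates that span dosing to the dosing date, unless the event had already resolved. Both help only when the onset is incompletely recorded. A Day 1 AE with a correctly recorded pre-dose time is excluded, while the same AE with the time left blank is included.
- Protocol 9.1.1 makes worsening of symptoms present at study start an AE in its own right. SAP 10.2.1 defines study start as the day of consent, so this covers conditions that predate consent. It does not clearly cover an AE that began between consent and dosing.

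**With a worsening clause added**, the case meets the TEAE rule, and the treatment-emergent SAE or AESI rule if it is serious or falls in an AESI category.

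**Laboratory.** An abnormality already present at baseline that moves to a worse category is not emergent if absence at baseline is judged per abnormality, but is emergent if judged per severity category. SAP 7.4.1 does not say which. The marked-abnormality definitions in Appendix C are redacted, so the text available cannot settle it. SAP 11.1 to 11.3 do not mention the added baseline condition.

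**The case against.** The strongest reply is that the SAP follows the protocol's prespecified rule, that safety is descriptive in a single-dose exploratory study, and that no test or decision rule changes. That is correct and limits the weight of the point. It does not supply a summary category for these events.

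A reader might go further and infer several things that the documents do not support:

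- **That such events disappear.** All AEs are listed with SAEs flagged, and there are separate SAE and AESI listings (SAP 7.2.2). SAEs reach the sponsor within 24 h whatever their classification (Protocol 9.2.2). The Safety Event Committee's focus on major bleeding within 3 days of dosing is not tied to the TEAE rule (Protocol 3.4).
- **That every worsening is missed.** The gap depends on a single record that keeps its pre-dose onset. Protocol 9.1.2 and SAP 7.2.1.4 point that way, but neither forbids a new entry, and CRF completion instructions are not in the documents.
- **That worsening of an existing mild anaemia goes unseen.** Clinically significant laboratory worsening is itself an AE under Protocol 9.1.1 and can be a TEAE if entered with a post-dose onset. Hematology changes from baseline are summarised regardless (SAP 7.4.2), and subjects with hemoglobin of 10 g/dL or less are excluded.
- **That about 324 subjects over 21 days measures the exposure.** Only AEs still ongoing at injection can qualify.
- **That the rule necessarily favours the drug.** It applies equally to placebo, where a bruise can also worsen. The loss is uneven only if the drug causes worsening.
- **That ECG worsening needs the same remedy.** SAP 7.5 already flags QT, QTcF and QTcB increases above 30 and above 60 ms from baseline.

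**Conclusion.** The gap is real but narrow. It concerns AEs with a recorded onset between consent and injection that are still ongoing at dosing, become more intense or serious within 48 h after it, and are held as one record. These are left out of the treatment-emergent AE, SAE and AESI summaries and of Table 5 altogether, and appear only in listings.

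The documents give no pre-dose AE rate, so the number cannot be calculated; it is probably small. The effect is an undercount of post-dose worsening in the safety summaries. The primary PD result is unaffected.

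This is a gap shared by the protocol and the SAP, not a departure of one from the other. The conclusion rests on the single-record reading of the intensity rules, which the documents suggest but do not state. The laboratory point is a request for clarification, because the grading appendix cannot be read.

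**What to change.** 1. In SAP 7.2.1.2, 7.2.1.6 and 7.2.1.9, define treatment-emergent as onset from injection to 48 h after it, or onset before injection with an increase in intensity or seriousness within 48 h after injection. Record this in SAP section 11 as a change from Protocol 10.2.3.1.
2. Confirm that the CRF dates each change in intensity or seriousness. The protocol says intensity changes are reported, not that they are dated. If they are not dated, require a post-dose worsening to be entered as a new AE record with its own onset.
3. In SAP 7.4.1, state that absence at baseline applies per severity category, so that a worse category than at baseline counts as emergent.

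The cost is SAP wording and one extra derivation from intensity changes the CRF already records, provided they are dated; otherwise there is also a data-entry instruction. TEAE counts may rise slightly. No new procedure for subjects is needed.
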